### 5.5.2 Qualification Phase (Part B)

For each qualification group, an unblinded statistician from INC Research, not otherwise involved in the study, will prepare a list of subject randomization numbers. These randomization numbers will be used to prepare individual subject doses. Sealed qualification code break envelopes will be available for each subject in case of emergency.

Upon completion of each group of subjects, the randomization codes for the completed subjects will be unblinded by the CRU pharmacy, and the eligibility of subjects to participate in the Treatment Phase will be assessed as described in Section 4.5.

### 5.5.3 Treatment Phase (Part B)

The only persons with access to the blinding schema during the Treatment Phase will be the designated pharmacy personnel who are responsible for the dispensing of study drug, the compliance auditor(s) who verify conformity to study procedures, and the unblinded statisticians who generate the code. Under normal circumstances, the blind will not be broken until all subjects have completed all treatments. During the Treatment Phase, blinded dosing information

will be broken only in an emergency where knowledge of dosing information could impact further treatment decisions or aid in the emergency treatment of a subject. Individual blinded dosing information can be broken by opening a subject's sealed code break envelope, thereby, not compromising the blind for the remaining subjects. Individual code breaks by the investigator or designee will result in the withdrawal of the subject from the study. The date, time, and reason for the unblinding will be documented in the appropriate section of the CRF and in the source documents.

## 5.6 Treatment Compliance

Study drugs will be administered under the supervision of study personnel and treatment compliance will be verified according to protocol requirements.

# 6. STUDY PROCEDURES AND ASSESSMENTS

All study assessments will be performed at the visits and time points outlined in the Time and Events Schedule (Section 3.1.7). Study drug administration will be considered as time zero. Other logistical considerations (eg, sequence of events, assessment windows) will be outlined in study-specific procedures.

## 6.1 Pharmacodynamic Assessments

All subjects will undergo a training and practice regimen prior to completion of the computerized subjective measures. Subjects will also receive PD refresher sessions prior to dosing in the Treatment Phase. Measures will be administered and data will be captured electronically using proprietary computerized software (PsychometRx®; INC Research Toronto, Inc.).

Testing conditions for PD assessments should remain as consistent as possible for each treatment period. Subjects will be monitored carefully to ensure that they are completing the assessments appropriately. See Section 9.4 for details regarding the anonymity of subject information.

### 6.1.1 Visual Analog Scale

Table 10 shows the VAS items administered in this study. Each VAS is scored as an integer from 0 to 100. The use of a unipolar or bipolar scale is determined by the nature of the subjective effect being measured. Unipolar VASs (eg, High, Good Drug Effects, Bad Drug Effects, Any Drug Effects, and Hallucinations) are presented with anchors such as "Not at all" (score = 0) to "Extremely" (score = 100), where the neutral point equals 0. Note that scales that refer specifically to drug (eg, Good Drug Effects, Bad Drug Effects, Any Drug Effects) are not administered pre-dose. When appropriate, VASs will be administered as bipolar measures, meaning that the neutral point equals 50 (eg, Drug Liking, Overall Drug Liking, Take drug Again, and Drowsiness/Alertness VAS). The neutral point will also be labeled with an anchor, such as "neither like nor dislike".

Eligible subjects who appear to have difficulty differentiating between bipolar and unipolar scales (eg, making errors such as selecting 50 as neutral for a unipolar scale) during the

Qualification Phase will undergo additional practice training on the difference between the scale types.

[figure not shown]
**Table 10 Description of Subjective Effects Visual Analog Scales**

Scale Interpretation	Exclude Pre-dose	Description	Question Text	Response Anchors
Balance	Yes	Drug Liking	At this moment, my liking for this drug is	0: Strong disliking 50: Neither like nor dislike 100: Strong liking
Global	Yes	Overall Drug Liking	Overall, my liking for this drug is	0: Definitely not 50: Neutral 100: Definitely so
Global	Yes	Take Drug Again	I would take this drug again	0: Definitely not 50: Neutral 100: Definitely so
Positive	Yes	Good Drug Effects	At this moment, I feel good drug effects	
Positive	No	High	At this moment, I feel high	0: Not at all
Negative	Yes	Bad Drug Effects	At this moment, I feel bad drug effects	
Other effects	No	Hallucinations	I am experiencing hallucinations	100: Extremely
Other effects	Yes	Any Drug Effects	At this moment, I feel any drug effect	
Other effects	No	Drowsiness/Alertness	At this moment, my mental state is	0: Very drowsy 50: Neither drowsy nor alert 100: Very alert

Scales have 5 possible interpretations: (1) "Positive" subjective effects, (2) "Negative" subjective effects, (3) the "Balance" between positive and negative effects, (4) "Other effects" (ie, pharmacologic effects that indicate an active substance, which may be perceived as either positive or negative depending on the context), and (5) "Global" (ie, end-of-day assessment or next day overall assessment).

The overall appearance of all VAS items is similar to the screen images below. [Figure 3A](#) presents the display for a typical question. Using a mouse, the subject must position the cursor over the small vertical box (a "slider") and click on it to move it left or right. To register the response, the subject must then press the "OK" button that appears below the horizontal line ([Figure 3B](#)). This multi-step procedure was designed to reduce the possibility of either accidental or automatic responding to such scales. The questions and anchors will be modified appropriately to reflect study-specific questions.

**Figure 3 Sample Screen Images for Visual Analog Scale Presentation**

#### 6.1.1.1 Drug Similarity VAS

The Drug Similarity VASs provide an estimate of the drug class with which drug users identify the test drug. The same VAS procedures used to assess subjective drug responses will be used to assess perceived drug similarity. Subjects will be asked to compare the drug they received to a comparison drug on a scale ranging from “Not at all similar” to “Very similar” (Table 11). Each scale is scored as an integer from 0 to 100, where the position of the subject’s response on the scale represents a defined integer. Drugs that a subject has not personally experienced often enough to use as a standard of comparison (based on the screening assessment) will not be included in his or her questionnaire.

**Table 11 Description of Drug Similarity Visual Analog Scales**

Description	Question Text	Response Anchors
Drug similarity	How similar is the drug you most recently received to [drug name] ? where the question will be repeated for each [drug name] in the following list:	0: Not at all similar 100: Very similar
Phencyclidine (PCP) Caffeine Cocaine (including crack) Codeine, morphine, oxycodone, hydrocodone, hydromorphone Ecstasy (MDMA) Heroin		
	LSD Methadone Nicotine Placebo D-amphetamine (“Speed”) or methamphetamine	Pseudoephedrine (Sudafed) Halcion, Xanax, or Valium Ketamine (“Special K”) THC (marijuana, cannabis, hash)
Overall Familiarity	At the conclusion of the list of specific drugs, a general question will appear: How familiar was the effect of the drug you most recently received?	0: Very unfamiliar 100: Very familiar

### 6.1.1.2 Bowdle VAS

The Bowdle VAS consists of 13 items for which the subject is asked to rate his or her current feelings. An adapted computerized version of Bowdle VAS will be administered with 11 items examining internal and external perception sub-scales. Each VAS will be scored from 0 to 100, with 0 reflecting “Not at all” and 100 reflecting “Extremely.” Lower individual and overall scores indicate fewer psychedelic effects.

The individual items of the questionnaire are listed below:

1. My body or body parts seemed to change their shape or position (BODY)
2. My surroundings seemed to change in size, depth, or shape (SURROUNDINGS)
3. The passing of time was altered (TIME)
4. I had feelings of unreality (REALITY)
5. It was difficult to control my thoughts (THOUGHTS)
6. The intensity of colors changed (COLORS)
7. The intensity of sound changed (SOUND)
8. I heard voices or sounds that were not real (VOICES)
9. I had the idea that events, objects, or other people had particular meaning that was specific for me (MEANING)
10. I had suspicious ideas or the belief that others were against me (SUSPICIOUS)
11. I felt anxious (ANXIOUS)

Items 1, 2, 3, 5, 6, and 7 are combined to assess the derived variable “subjective external perception.” Items 4, 8, 9, 10, and 11 are combined to assess the derived variable “subjective internal perception.”

If one of the items is missing, the related score will not be calculated.

### 6.1.2 Divided Attention Test

[figure not shown]
The Divided Attention Test (DAT) is a manual-tracking test with a simultaneous visual target detection component. The subject is provided with a joystick with a trigger to execute this measure. During testing, the subject is presented with the image of an airplane and a randomly curving road (Figure 4). As the road moves down the screen, the subject is to try and position the image of the airplane over the center of the road. At random times during this process, a visual target will briefly present itself at random positions on the screen and immediately disappear. The subject is to respond to the visual target as fast as possible by pressing a button on the joystick. There are 16 targets presented during each trial. Each test consists of three 1-minute trials over different road courses. Performance is measured based on the subject’s ability to keep the image of the airplane over the road, and the subject’s ability to respond to the visual target.

The following outcome measures will be used to assess performance on this task:

- Root mean square (RMS) distance: the RMS distance from the center of the road (pixels)
- Greatest distance: the maximum distance from the center of the road (pixels)

- Response latency of correct responses (msec)
- Average number of false alarms
- Percentage over road: percentage of time over the road (%)
- Percentage of target hits (%)

[figure not shown]
**Figure 4 Sample Screen Image for the Divided Attention Test**

### 6.1.3 Digit Symbol Substitution Test

The Digit Symbol Substitution Test (DSST) (modified) is a test of processing speed and visual-motor coordination. Subjects are presented with a legend or key at the top of the screen, which shows 10 digits displayed with 10 different associated symbols (Figure 5A). Just below the center of the screen, a single digit appears with a  $3 \times 3$  grid of 9 squares presented below. Inside the grid, subjects must draw the symbol associated with the digit displayed on the screen (Figure 5B). When they have drawn the appropriate symbol, a new single digit and workspace appear. The goal is for the subject to complete as many symbols correctly as they can in the amount of time determined in the measure configuration (typically 90 seconds). Each time subjects perform this task, the same 10 symbols will be used, but the order of the symbols across the top of the screen and the corresponding digit will change. The task is scored for the number of symbols completed and the number of errors (symbols completed incorrectly).

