### 2.2.3.1 Pharmacodynamic Endpoints

- Balance of effects:
  - Drug Liking VAS ( $E_{\min}$ , time to maximum/minimum effect [ $TE_{\max}/TE_{\min}$ ], and time-averaged area under the effect curve [TA\_AUE])
- Positive drug effects:
  - High VAS ( $E_{\max}$ ,  $TE_{\max}$ , and TA\_AUE)
  - Good Drug Effects VAS ( $E_{\max}$ ,  $TE_{\max}$ , and TA\_AUE)
- Negative drug effects:
  - Bad Drug Effects VAS ( $E_{\max}$ ,  $TE_{\max}$ , and TA\_AUE)
- Other effects:
  - Hallucination VAS ( $E_{\max}$ ,  $TE_{\max}$ , and TA\_AUE)
  - Any Drug Effects ( $E_{\max}$ ,  $TE_{\max}$ , and TA\_AUE)
  - Drowsiness/Alertness VAS ( $E_{\min}$ ,  $TE_{\min}$  and TA\_AUE)
  - Bowdle VAS ( $E_{\max}$ ,  $TE_{\max}$ , and TA\_AUE)
  - Drug Similarity VAS (score at 12 hours)
- Objective measure:
  - Pupillometry (maximum pupil constriction [MPC], time to MPC [TMPC], and time-averaged pupillometry area over the curve [TA\_PAOC])
- Cognitive and psychomotor effects:
  - Divided Attention Test (DAT)
    - Root mean square (RMS) distance: the RMS distance from the center of the road (pixels) ( $E_{\max}$ )
    - Percentage over road: percentage of time over the road (%); ( $E_{\min}$ )
    - Greatest distance: the maximum distance from the center of the road (pixels) ( $E_{\max}$ )
    - Response latency of correct responses (msec) ( $E_{\max}$ )
    - Average number of false alarms ( $E_{\max}$ )
    - Percentage of target hits (%) ( $E_{\min}$ )
  - Digit Symbol Substitution Test (DSST)
    - Number of symbols completed ( $E_{\min}$ )
    - Number of errors (symbols completed incorrectly) ( $E_{\max}$ )

- Sternberg Short-Term Memory Test (SSTM)
  - d'Prime (d') pooled, for all valid responses ( $E_{min}$ )
  - Mean reaction time pooled, for all valid responses ( $E_{max}$ )

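### The raw DSST error count depends on how many symbols were completed, so it can hide or reverse a loss of accuracy; number correct and a pooled error rate should be specified before Part B

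*Protocol*

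**What the plan says.** Protocol Section 6.1.3 states the aim of the DSST: "The goal is for the subject to complete as many symbols correctly as they can". The test length is set in advance, usually 90 seconds, so the number attempted depends on speed. The same section says "The task is scored for the number of symbols completed and the number of errors (symbols completed incorrectly").

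Section 2.2.3.1 lists two DSST endpoints: number completed, taken at its minimum, and "Number of errors (symbols completed incorrectly"), taken at its maximum. Neither document defines a number correct or an error rate for this test. The other two cognitive tests each have an accuracy measure on a fixed base. The Divided Attention Test (DAT) has "Percentage of target hits", with 16 targets per trial (Section 6.1.2). The Sternberg test (SSTM) has "d'Prime (d') pooled, for all valid responses", with 24 probes per list (Section 6.1.4).

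Under Section 8.1.3, endpoints that are neither primary nor key secondary are tested against a difference of zero, two-sided at 0.05, without multiplicity adjustment. The SAP (Sections 2.1 and 5) covers Part A only and adds no DSST derivation.

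**The concern.** The score that the task is built to produce, symbols correct, is not an endpoint. The two analysed scores do not replace it. Number completed includes wrong symbols. The error count mixes accuracy with speed: a subject who attempts fewer symbols has fewer chances to err. The minimum of one count and the maximum of the other may also come from different times, so the two summary values cannot be combined into a number correct.

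Cognitive and psychomotor effect is the first secondary objective of Part B (Section 2.1.2). Somnolence is listed among the common adverse events of nalbuphine (Section 1.1) and sedation among those of hydromorphone (Section 3.2.1). Slowed output is therefore plausible in the arms being compared. A result of fewer errors than placebo could be reported as statistically significant when accuracy was unchanged or worse.

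**Working it through.** The documents give no DSST output, error rate, SD or effect size, so there is no stated figure to reproduce. All rates below are assumptions. The number of tests is taken from Table 3: 15 post-dose DSST times per period (0.5 to 24 hours).

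**Break-even, one test.** Expected errors = n × p, where n is symbols completed and p is the error rate. If a dose changes n to n(1-c) and p to mp, expected errors become np × m(1-c). This is below placebo whenever m < 1/(1-c).

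- c = 20%: 1/0.8 = 1.25
- c = 30%: 1/0.7 = 1.43
- c = 50%: 1/0.5 = 2.00

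Example at break-even: 50 × 0.04 = 2 errors, and 25 × 0.08 = 2 errors. The error rate has doubled and the count shows no difference.

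**Emax over 15 tests, binomial simulation.** Assumed placebo: 50 symbols at 4% errors throughout. Assumed sedating profile: 25 symbols at 6% for 8 tests, 35 at 5% for 4, then placebo level for 3.

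| | Placebo | Sedating profile |
|---|---|---|
| Mean Emax of errors | 4.68 | 4.16 |
| Mean Emin of number correct | 45.3 | 21.7 |
| Pooled error rate | 30/750 = 4.0% | (12 + 7 + 6)/490 = 5.1% |

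The raw count favours the dose by 4.68 - 4.16 = 0.52 errors while its accuracy is worse. If the rates are 8% at the 8 slowest tests and 6% at the next 4, mean Emax is 4.68, equal to placebo, although the pooled rate is (16 + 8.4 + 6)/490 = 6.2%.

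**Other inputs.** Assumed 40 symbols on average (Poisson), 5% errors, and a 30% output cut. Mean Emax of errors on placebo is 4.77.

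| Error rate multiplied by | Sedated to 4 h (6 tests) | To 9 h (13 tests) | To 24 h (15 tests) |
|---|---|---|---|
| 1 | 4.46 | 3.95 | 3.75 |
| 1.25 | 4.61 | 4.41 | 4.35 |
| 1.5 | 4.83 | 4.91 | 4.92 |
| 2 | 5.42 | 5.91 | 6.02 |

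The first two rows fall below placebo and the last two rise above it, as the break-even of 1.43 predicts. The direction is the same at baseline error rates of 2% and 10%. In these profiles Emin of number completed falls from 29.4 to about 19 to 21.

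**Which accuracy measure to use.** The Emax of a per-test error percentage is not a safe replacement. With the first sedating output profile and the error rate held at 4%, its mean is 11.2%, against 9.4% on placebo, because a smaller denominator makes the largest percentage more variable. With the worsened rates it is 13.9%. So 1.8 points (11.2 - 9.4) of the 4.5-point gap (13.9 - 9.4) appear with no change in accuracy. The pooled rate, total errors over total completed, stays at 19.6/490 = 4.0% when accuracy is unchanged and moves to 5.1% when it worsens.

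**The case against.** The best defence is that the plan does not rely on the error count alone. Number completed is a listed endpoint and would show the slowing: in the first profile it halves, from 50 to 25. Section 8.1.3 summarises pharmacodynamic data at every time point and reads abuse potential from the pattern across measures. Six DAT and two SSTM endpoints stand beside the DSST. Slower output with fewer errors is a recognisable trade of speed for accuracy. This largely stands, and it limits the harm. It does not restore the accuracy information, because the planned summaries are of two separate counts and neither shows whether accuracy changed.

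A second objection is that the profiles are severe. Section 12.2 reports mild events in Part A up to 162 mg, with Grade 1 somnolence in 2 of 6 subjects at 81 mg. That is fair for those doses, but Part B adds hydromorphone and may use higher nalbuphine doses. With a milder profile (a 20% cut over 6 of 15 tests, error rate 1.5-fold) mean Emax is 4.96 against 4.68, so the raw count does show the impairment.

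A reader might infer that any sedating dose must show fewer errors. The documents do not support this: it depends on the error rate rising by less than 1/(1-c), and they hold no data on that. Short sedation also weakens the effect, because recovered tests can set the peak.

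A reader might also extend the point to the SSTM reaction time. That does not follow. Each SSTM list has a fixed 24 probes, so accuracy there does not depend on output, and the protocol does not define a valid response, so the inclusion of wrong answers cannot be established.

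**Conclusion.** The point holds as a possibility. The raw DSST error count, tested on its own at two-sided 0.05, can hide or reverse a loss of accuracy when a dose also cuts output. The break-even ratio 1/(1-c) is arithmetic and needs no data. The size is illustrative: about half an error in the first profile, and 0.16 to 0.42 errors (4.77 - 4.61 to 4.77 - 4.35) for a 30% cut with a 1.25-fold error rate. These figures rest on assumed output, error rates and duration of sedation.

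The weight is low. The DSST is among the other secondary endpoints of Part B, and the primary endpoint, the sample size and the error rate of the main tests are unaffected. Nothing is lost at collection, because both counts are recorded at every test. The SAP says Part B had not started, so the change can be made before any Part B data exist.

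**What to change.** In the Part B analysis plan, and in Protocol Section 2.2.3.1 if it is amended:

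1. Derive number correct (completed minus errors) at each time point, and analyse its Emin as the main DSST endpoint.
2. Assess accuracy as total errors divided by total symbols completed over the post-dose tests of each period. Do not use the Emax of a per-test percentage.
3. Keep the raw error count as descriptive only, shown beside number completed.

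The cost is one or two extra derived variables, with no change to conduct. The pooled rate dilutes short-lived effects: in the milder profile above, 6% at the sedated tests becomes (14.4 + 18)/690 = 4.7% pooled. The by-time summaries should therefore stay beside it.

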**Figure 5 Sample Screen Image for the Digit Symbol Substitution Test**

#### 6.1.4 Sternberg Short-Term Memory

The Sternberg Short-Term Memory (SSTM) task is a measure of immediate memory in which subjects are asked to remember a series of digits that are rapidly presented on a computer screen.

The SSTM task involves rapid presentation of target lists of 2, 4, and 6 stimulus digits (1.2 seconds/digit). Two seconds after presentation of each list of digits, a series of 24 probe digits is presented. The subject is to identify as quickly as possible whether or not each probe appeared in the target list by pressing buttons on a response box meaning “YES” or “NO.” Probes that appeared on the target list are called “positive”, while probes that did not appear on the target list are called “negative.”

The test consists of 3 trials with digit sequence size lengths of 2, 4, and 6. Performance is assessed by measures of response latency and accuracy.

#### 6.1.5 Pupillometry

Pupillometry will be used as an objective physiological PD measure as it is a sensitive measure of central opioid/stimulant action and appears to be resistant to tolerance development with repeated administration. An electronic pupillometer (NeuroOptics) will be used to measure pupil diameter. Data from a series of frames will be used in the calculation, and the final display will show the weighted average and standard deviation (SD) of the pupil size. Measurements will be collected under mesopic lighting conditions. For each subject, every effort will be made to use the same eye for all assessments throughout the study.

## 6.2 Pharmacokinetic Assessments

In Part A and Part B, venous blood samples (2 mL) will be collected to determine the plasma concentrations of nalbuphine following oral administration of nalbuphine solution and nalbuphine ER tablet. Samples will be collected, processed, and shipped according to the

instructions provided in the laboratory manual and instructions from the sponsor or bioanalytical laboratory.

The PK sample collection timepoints are included in [Table 1](#) for Part A and [Table 3](#) for Part B. Blood volumes required for PK sampling are available in [Appendix 11.1](#) (Part A) and in [Appendix 11.2](#) (Part B).

The plasma samples will be analyzed for nalbuphine and metabolites by Covance using validated methods.

Plasma samples will be shipped frozen on dry ice from the research site to Covance at the address provided in the laboratory manual. Samples will not be shipped without prior arrangement with the bioanalytical laboratory and notification to the sponsor.

Drug concentration information that may unblind the study will not be reported to the study site or blinded personnel until the study has been unblinded.

